18 DEC 2017

Date

Name: [name]. [name]

Co-Investigator

23-11-2017

Date

Name: [name]. [name]

Table of Contents

Table of Contents	3
1. Study Synopsis.....	5
2. Background, rationale and novelty	7
3. Trial objectives and design	8
3.1 Preparation, organization and management of phase 1 study.....	9
3.2 Preparation, organization and management of phase 2 study.....	12
3.3 Preparation, organization and management of longitudinal follow-up	13
4. Selection and withdrawal of subjects	15
4.1 Inclusion criteria	15
4.2 Exclusion criteria	15
4.3 Expected duration of trial.....	16
5. Trial procedures.....	16
5.1 MRI and ¹⁸ F-flutemetamol PET-CT scans.....	16
5.2 Sample collection and handling	16
5.3 Genetic analysis.....	16
5.4 Fasting laboratory test analysis.....	16
5.5 Ocular exams	16
5.6 Summary of visits/procedures	17
5.7 Supervision and responsibilities	17
5.7.1 Insurance	18
5.7.2 Informed consent	18
6. Assessment of efficacy	18
7. Assessment of safety.....	18
8. Statistics	19
8.1 Sample size	19

8.2 Analysis.....	19
9. Quality assurance	19
10. Direct access to source data and documents.....	19
11. Ethics and regulatory approvals.....	19
12. Data Handling	20
13. Data Management.....	20
14. Translational research.....	20
15. Publication Policy	21
16. Financial Aspects	21
17. References.....	22

1. Study Synopsis

Title of clinical trial	Multimodal retinal imaging in the detection and follow-up of Alzheimer's disease
Protocol Short Title/Acronym	RetAD
Sponsor name	UZLeuven
Principal Investigator	[name]. [name]
Medical condition or disease under investigation	Alzheimer's disease
Purpose of clinical trial	To evaluate the use of non-invasive, multimodal retinal imaging for the early detection of Alzheimer's disease and for the evaluation of disease progression
Primary objective	To identify retinal biomarkers for Alzheimer's disease by means of non-invasive, multimodal retinal imaging
Secondary objective(s)	
- To evaluate the diagnostic performance of selected ocular biomarkers for Alzheimer's disease- To deliver a proof-of-concept for the use of retinal biomarkers to quantitatively measure cerebral Aβ load

	
- To deliver a proof-of-concept for the use of retinal biomarkers to follow Alzheimer's disease progression
Trial Design	Observational, cross-sectional and prospective cohort
Endpoints	
- Technical capability to detect Alzheimer's disease by means of non-invasive retinal imaging- Technical capability to follow up Alzheimer's disease progression by means of non-invasive retinal imaging
- If acceptable technical capability demonstrated: determination of diagnostic accuracy of multimodal retinal imaging in Alzheimer's disease (sensitivity and specificity)
Sample Size	90 individuals (35 amyloid-negative, 55 amyloid-positive)
Summary of eligibility criteria	
• Age between 50 and 85• In stable medical condition and willing and able to perform study procedures.• Fluent in written and verbal Dutch.• Capable of giving informed consent.
Maximum duration of treatment of a subject	/
Version and date of final protocol	v 1.2 27/10/2017
Version and date of protocol amendments	

2. Background, rationale and novelty

Alzheimer's disease (AD) is the most common neurodegenerative disorder and the leading cause of dementia worldwide.¹ A growing number of people are surviving into their 80s-90s and the number of AD patients projected to nearly triple in the next three decades, affecting 80-90 million people worldwide by 2040.^{1,2} As such, AD will become the third cause of death for older people, just behind cardiovascular disease and cancer. In contrast to the latter, AD cannot be prevented, slowed or cured. AD represents an enormous socio-economic burden and has become a trillion dollar disease.³ Despite decades of intensive research, diagnosis and treatment remain challenging for AD. A string of recent failures in clinical trials for AD drugs has pointed out that our understanding of the disease is still far from complete. More in detail, three major reasons underlying this treatment gap have been identified:

- i. **The lack of techniques for patient screening and early diagnosis.**
- ii. **The incomplete understanding of the complex interplay of pathological processes that underlie AD.**
- iii. **The many hurdles between drug discovery and approval.**

With this study, we propose a novel way to address these needs, by using the retina as a model organ to study the central nervous system (CNS). Many of the hallmark cerebral pathophysiological processes of AD have also been observed in the retina. Unlike the rest of the CNS, the retina can be visualized directly, with an imaging resolution up to 100x higher than PET and MR scans. Using these high-resolution imaging tools such as Optical Coherence Tomography (OCT), studies have demonstrated microvascular changes and neuro-retinal thinning in AD patients. Pilot data show that retinal A β can be visualized non-invasively solely based on the intrinsic hyperspectral signature of aggregated amyloid deposits.⁴ Non-invasive retinal imaging (e.g., fundus photography, OCT, hyperspectral imaging (HSI)) – which are all available at affordable cost –, could therefore represent novel means for identifying patients at risk, for longitudinal follow-up of disease progression in AD patients, and for research in a quest for more effective treatments.

3. Trial objectives and design

The ambition of this study is to contribute to AD diagnosis and clinical research via noninvasive multimodal imaging of the retinal manifestation of AD. It aims to respond to four problems that are currently being faced within the AD research field, by delivering a proof-of-concept for the use of multimodal imaging of retinal biomarkers for diagnosis and disease staging of AD, thereby tackling:

1. the lack of an affordable, multimodal retinal imaging platform for clinical research and practice;
2. the difficulties in recruiting A β -positive presymptomatic patients for phase III clinical trials;
3. the need for non-invasive markers to monitor disease progression from a presymptomatic stage of the disease onwards;
4. the lack of integrative prognostic software for disease identification.

The main contribution will consist of the examination of the validity of retinal biomarkers as a diagnostic measure for A β -positivity, and the determination of their ability to quantitatively measure change in A β load. At the end of the project, we aim to deliver a research setup of a hyperspectral camera for retinal imaging, standardized image acquisition protocols for retinal imaging of AD biomarkers using different technologies (including hyperspectral imaging) and a data science approach for AD diagnosis. Proof-of-concept for the predictive value of multimodal imaging of selected retinal biomarkers in diagnosing and classifying AD patients will be delivered.

This may be in the future useful for screening, early diagnosis and follow-up of AD. This is of major importance because AD has a long preclinical and prodromal phase, and by the time symptoms suggestive of a clinical diagnosis appear, neurodegeneration may have led to damage too extensive to repair.

The primary objective of the human clinical diagnostic trial is to validate the retinal biomarkers against A β load measured with ^{18}F -flutemetamol PET as standard-of-truth. The cross-sectional data collection is mainly aimed at exploring retinal biomarkers as a diagnostic measure for A β -positivity, while gathering the longitudinal information is mainly aimed at determining their ability to quantitatively measure change in A β load. The discriminative value of retinal imaging will be assessed (phase 1) and

subsequently evaluated (phase 2). All patients will be followed longitudinally over the course of 24 months.

This is an open-label longitudinal biomarker study without investigational medicinal product in subjects in different stages of the AD spectrum.

The data that we will collect consist of amyloid imaging, MRI, blood, genetic, general health and cognitive data, as well as visual acuity, ocular biomicroscopy and funduscopy, fundus photographs, hyperspectral retinal images, Optical Coherence Tomography (OCT) retinal images and OCT angiography (OCT-A) retinal images. Subjects will be followed longitudinally. In the current study we will primarily investigate the potential of non-invasive, multimodal retinal imaging for the early detection of Alzheimer's disease and for the evaluation of disease progression. This will be done in comparison with amyloid imaging and neuropsychological evaluations.

We will build a **longitudinal database** of ocular, systemic, neuro-psychiatric, MRI and PET imaging parameters of A β -positive and A β -negative patients with different stages of cognitive impairment. This database will be used to provide proof-of-concept that retinal biomarkers provide an early, accurate and non-invasive tool for AD detection and follow-up. All data will be collected in a database for statistical analysis.

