3.1 Preparation, organization and management of phase 1 study

The primary objective of this exploratory phase 1 study is to evaluate which ophthalmological measures optimally differentiate between A β -positive, clinically probable AD patients and A β -negative, cognitive-intact healthy controls, matched for age, education, gender and apoE status.

Methodology

Study cohorts:

1. Fifteen clinically probable AD patients, according to the National Institute of Aging (NIA)-Alzheimer's Association (AA) diagnostic criteria,⁵ with an MMSE of 12 or higher, and with a positive CSF biomarker analysis or a positive amyloid-PET scan in the past or a positive amyloid-PET scan at inclusion, will be included in this group. Patients will be recruited via the memory clinic UZ

Leuven, which is headed by Prof. dr. [name] (total number of dementia patients due to AD currently in follow-up = 486).

2. Fifteen A β -negative cognitive-intact healthy controls will be recruited from a longitudinal cohort of 180 cognitively healthy older adults who are followed at the Laboratory for Cognitive Neurology of Prof. dr. [name] (UZ Leuven) (mean age = 68.4 \pm 6.4, range 55-80 years).^{6,7} These community-dwelling participants were first recruited between 2010 and 2015 for multimodal brain imaging (A β PET and volumetric MRI) combined with neuropsychological assessment. One of the key inclusion criteria was neuropsychological test scores within the published norms at baseline. This cohort has been well characterized at baseline by means of detailed evaluation of lifestyle factors (lifelong cognitive and physical activity), quantitative parameters (weight, height, blood pressure under standardized conditions), cognitive reserve score (Cognitive Reserve Questionnaire), and neuropsychological performance. Participants are longitudinally followed with neuropsychological assessments at two-yearly intervals. The ready availability of this deeply phenotyped cohort is a strength of this project.

A β -negative cognitive-intact controls will be matched to the AD patients for age, gender, education and apoE status. The A β -negative status and the cognitive-intact status will be verified by a repeat A β PET scan and a neuropsychological assessment at inclusion in the current study.

Study procedures:

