After signing the informed consent, patients will be asked to fill in a questionnaire. All eligible participants will then undergo detailed ophthalmological examination, an MRI scan, ¹⁸F-flutemetamol PET scan, blood sampling (apoE genotyping and fasting laboratory tests – Table 1), as well as a detailed neuropsychological assessment.

Hematology	Chemistry	Genotyping
Hematocrit	Gamma GT	apoE polymorphism
Hemoglobin	Alkaline phosphatase	
Platelet count	Alanine aminotransferase (ALT)	
WBC (total and differential)	Aspartate aminotransferase (AST)	

Sedimentation rate	Bicarbonate	
	Calcium	
	Chloride	
	Potassium	
	Sodium	
	Creatinin	
	Urea	
	Low-density Lipoprotein	
	C-reactive protein	
	Glycemia	
	HbA1c	

Table 1: Laboratory tests

- Ophthalmological examination will include visual acuity measurement, biomicroscopy and funduscopy, followed by the acquisition of hyperspectral, (angio-) OCT, and fundus photography using predetermined protocols.
- PET images will be acquired on a TruePoint Siemens PET scanner using static acquisition during an acquisition window of 30 minutes, starting 90 minutes post-injection. A low-dose computed tomography scan will be performed for attenuation correction, prior to the PET scan. The summed ¹⁸F-flutemetamol PET image (sumPET) will be co-registered to the subjects' T1-weighted MRI image. Segmentation parameters from the subjects T1-weighted MRI will be used to normalize the co-registered sumPET. A Standardized Uptake Value Ratio (SUVR) image will be created by dividing the normalized sumPET image by the uptake in the cerebellar grey matter reference region. SUVR values will then be calculated in a composite volume of interest (VOI) (SUVRcomp), consisting of frontal, parietal, anterior cingulate, posterior cingulate and lateral temporal VOIs, masked by the subject-specific gray matter map.⁶
- MRI will be performed on a 3T Achieva dstream Philips MRI scanner with a 32-channel head coil. The MRI sequence will consist of an MPRAGE volumetric MRI, and a FLAIR and Gradient Echo sequence.

- The Neuropsychological test battery will consist of the Auditory Verbal Learning Test (AVLT), Repeatable Battery for the Assessment of Neuropsychological Status (RBANS), Raven's Progressive Matrices (RPM), Mini Mental State Examination (MMSE), Neuropsychiatric Inventory (NPI), and Cornell Scale for Depression in Dementia (CSDD).

Statistical analysis:

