The primary statistical analysis will be based on a Receiver Operating Characteristic analysis of the different ophthalmological measures, to determine which have the best diagnostic accuracy (area under the curve) compared to the binary A β PET classification as standard-of-truth. In the cross-sectional studies, the standard-of-truth will consist of the binary distinction between A β -positive cases and A β -negative cases, based on A β PET. This distinction will rely on a semi-quantitative analysis and a cut-off based on independent data.⁷ The phase 1 study is considered exploratory and the diagnostic accuracy of a wide range of ophthalmological parameters will be assessed. The three ophthalmological parameters with the best diagnostic accuracy will be selected as primary outcome measures for further validation in the phase 2 study in an independent cohort.

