5.7 Supervision and responsibilities

The study will be performed under the supervision of Profs. [name] and [name], UZ Leuven. The local study nurses will coordinate the logistics and take the blood samples. Ocular exams and retinal imaging will be performed by MD PhD students skilled with the procedures. The participating investigators will perform their part of the study fully in accordance with the terms of the Protocol, the applicable national laws (amongst others: the Belgian Law of May 7, 2004 relating to experiments on human persons; the Belgian Law of August 22, 2002 on Patient Rights; the Belgian Law of December 8,

1992 (as amended) regarding the Protection of Privacy in relation to the Processing of Personal Data.) and apply and adhere to regulations and rules as, amongst others, the Declaration of Helsinki (2008) and ICH GCP Guidelines.

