8.2 Analysis

Cfr. Paragraph 3.

9. Quality assurance

To assure maximal quality and reproducibility, the trial protocol will be followed rigorously.

10. Direct access to source data and documents

Only data gathered in the context of the trial will be used.

11. Ethics and regulatory approvals

The trial will be conducted in compliance with the principles of the Declaration of Helsinki (2008), the principles of Good Clinical Practice and in accordance with all applicable regulatory

requirements. This protocol and related documents will be submitted for review to Ethics Committee of the University Hospitals Leuven.

The Study will be conducted only on the basis of prior informed consent by the Subjects to participate in the Study. We shall obtain a signed informed consent form (ICF) for all patients prior to their enrollment and participation in the Study in compliance with all applicable laws, regulations and the approval of the (local) Ethics Committee, if required. We shall retain such ICFs in accordance with the requirements of all applicable regulatory agencies and laws.

12. Data Handling

We shall treat all information and data as confidential and shall not disclose such information to any third parties or use such information for any purpose other than the performance of the Study. The collection, processing and disclosure of personal data, will comply with applicable personal data protection and the processing of personal data (Directive 95/46/EC and Belgian law of December 8, 1992 on the Protection of the Privacy in relation to the Processing of Personal Data). We will protect the data from disclosure outside the research according to the terms of the research protocol and the informed consent document. The subject's name or other identifiers will be stored separately from their research data and replaced with a unique code to create a new identity for the subject.

13. Data Management

All data will be analyzed and stored in a coded fashion, with a unique anonymous identifier for every subject. In the future, these data could be used in the context of this project, and for related projects regarding cognitive functions, Alzheimer's disease and related conditions.

14. Translational research

From every included patient, a blood sample will be collected and stored for genotyping and biochemical analysis.

15. Publication Policy

Any publication will be submitted to all co-authors at least thirty (30) days prior to submission or disclosure.

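### Nothing in the protocol masks retinal image acquisition or processing to amyloid status or clinical group, so measures that involve judgement could look more accurate than they are in both phases

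*Protocol*

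**What the plan says.** Section 3 presents the study as a diagnostic validation with flutemetamol PET as the truth standard, and classifies it thus: "This is an open-label longitudinal biomarker study without investigational medicinal product in subjects in different stages of the AD spectrum".

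On the retinal side, section 5.7 assigns the work: "Ocular exams and retinal imaging will be performed by MD PhD students skilled with the procedures". Section 3.1 describes the eye examination as visual acuity, biomicroscopy and funduscopy, "followed by the acquisition of hyperspectral, (angio-) OCT, and fundus photography using predetermined protocols". Section 5.5 only refers back to section 3.

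On group membership, section 3.1 lets the AD patients qualify "with a positive CSF biomarker analysis or a positive amyloid-PET scan in the past or a positive amyloid-PET scan at inclusion". Section 3.2 gives the same routes for the MCI patients and for the amyloid-positive intact adults. The AD and MCI patients come from the memory clinic. The intact adults come from a cohort recruited in 2010-2015 for imaging that included amyloid PET, in which 30 of 180 were positive at inclusion.

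On the reference side, section 3.1 says of the PET classification: "This distinction will rely on a semi-quantitative analysis and a cut-off based on independent data".

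On use of the measurements, section 3.1 says that in phase 1 "the diagnostic accuracy of a wide range of ophthalmological parameters will be assessed", and then: "The three ophthalmological parameters with the best diagnostic accuracy will be selected as primary outcome measures for further validation in the phase 2 study".

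On data handling, section 13 says: "All data will be analyzed and stored in a coded fashion", with one anonymous identifier per subject. Section 12 says that names are held apart from the research data.

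**The concern.** In a diagnostic accuracy study the index test should be read without knowledge of the reference result. With no study drug there is no treatment label to conceal, so what remains open is clinical group and amyloid status. If the person who repeats an acquisition, discards an image, adjusts a layer boundary or chooses a region knows the group, those choices can drift towards the expected answer.

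The two-phase structure does not protect against this. Phase 1 ranks many parameters by AUC and keeps the best three, which can favour the measures most open to judgement. Phase 2 uses an independent cohort, and that corrects the optimism from selecting the best of many. It does not correct a measurement bias that recurs because the same measures are taken under the same conditions. At stake are the choice of the three parameters and the sensitivity and specificity reported for them.

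**Working it through.** **1. Is masking provided anywhere?** The provisions that come nearest are these.

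| Provision | What it does | Does it withhold group from the image reader? |
|---|---|---|
| Predetermined acquisition protocols (3.1) | Standardises how images are taken | Not stated |
| Named, skilled examiners (5.7) | Sets who does the work | Not stated |
| Coded storage and analysis (12, 13) | Separates identity from data | Not stated; a code can sit beside group and PET fields, and section 3 plans one database for ocular, clinical and PET data |
| Semi-quantitative PET with an independent cut-off (3.1) | Limits judgement in the reference standard | No; it acts on the PET side only |

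**2. Can status be known before the eye examination?**
- AD and MCI patients: yes for those who enter on a past CSF or PET result. Memory-clinic recruitment also points to clinical group.
- Amyloid-positive intact adults: yes for those who enter on a past result.
- Amyloid-negative intact adults: they come from the same scanned cohort, so an earlier PET result exists. In phase 1 it is verified by a repeat scan at inclusion.
- Participants first found positive at inclusion: it depends on the order of tests. Section 3.1 lists the eye examination before MRI and PET but does not fix an order.

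Status can therefore be known for many participants, but is not shown to be known for all.

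**3. The plan's own effect size.** Section 8.1 gives at least 13 per group for phase 2 (effect size 1.33, alpha 0.05, power 0.90).
- Normal approximation: 2(1.960 + 1.282)² / 1.33² = 11.9, so 12.
- Two-sided t-test: 12.92, so 13, with power 0.902. At the planned 20 per group, power is 0.984.

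The figure reproduces, so d = 1.33 is used below as a standardised difference.

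**4. Illustrative size of bias.** Assumption, not in the documents: measurement with group known adds a shift b of 0.1 to 0.3 SD between groups. Under an equal-variance binormal model,

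AUC = Φ((d + b)/√2), and sensitivity = specificity = Φ((d + b)/2) at the midpoint cut-off.

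| b (SD) | AUC, d = 0 | AUC, d = 1.33 | Sens = spec, d = 0 | Sens = spec, d = 1.33 |
|---|---|---|---|---|
| 0 | 0.500 | 0.827 | 0.500 | 0.747 |
| 0.1 | 0.528 | 0.844 | 0.520 | 0.763 |
| 0.2 | 0.556 | 0.860 | 0.540 | 0.778 |
| 0.3 | 0.584 | 0.875 | 0.560 | 0.792 |

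Example: d = 1.33 and b = 0.3 give Φ(1.63/1.414) = Φ(1.153) = 0.875.

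With no true difference and 20 per group, a two-sided t-test at 0.05 would be significant with probability 0.061, 0.095 and 0.152 for b = 0.1, 0.2 and 0.3. Phase 2 is analysed by contingency table, so these probabilities only show scale.

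**The case against.** The strongest reply is that the protocol never says readers are unmasked. The open-label sentence can be read as a remark about treatment, and reading rules might sit in the acquisition protocols, which are not shown. It is correct that non-masking is an inference from that label plus silence. A reader might conclude that the protocol prescribes unmasked reading; the text does not go that far. The point still stands, because who sees what during image reading is study conduct. It has to be fixed before the first examination, and nothing in this protocol prevents reading with the reference result known.

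A reader might also infer that amyloid status is known for everyone before imaging. The documents do not support that. A positive scan at inclusion is an allowed route, and in the main phase 2 comparison both groups are cognitively intact members of one cohort, so neither presentation nor recruitment route reveals status. This narrows the concern, and it also shows where masking is easiest.

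Third, image rejection, boundary correction and region choice are not described in the protocol, which speaks of a data-science approach and does not say which outputs are automated. For most exploratory parameters it also gives no expected direction. This is accepted: the concern applies to measures that do involve judgement, and the bias is possible rather than certain.

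Fourth, the assumed shift is small against sampling error. At 20 per group the Hanley-McNeil standard error of an AUC of 0.83 is about 0.066, while the shift adds about 0.02 to 0.05. That is true, but a bias in one direction does not average out and is not reflected in a confidence interval.

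Finally, analysis under code is already planned and the PET classification is semi-quantitative with an outside cut-off. The second point stands: the documents do not support a matching concern about the reference standard. The first helps with the fix, but a subject code alone does not withhold group.

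**Conclusion.** The point holds in a limited form. The protocol labels a diagnostic validation study open-label, and nowhere keeps those who acquire or process retinal images from knowing amyloid status or clinical group, although that knowledge can be available beforehand for many participants. Coding and acquisition protocols do not ensure masking. Retinal measures that involve judgement could be favoured in the phase 1 selection and again appear too accurate in phase 2.

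The size is unknown. The AUC changes shown (0.50 to 0.53-0.58, and 0.83 to 0.84-0.88 at d = 1.33) rest entirely on the assumed 0.1 to 0.3 SD shift and the binormal model. Fully automated outputs are less exposed. The documents do not show that accuracy will be inflated, only that the design leaves this open. It is worth correcting before the first examination, because the remedy is cheap and unmasked readings are hard to repair later.

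**What to change.** Add a paragraph to sections 3.1 and 3.2, and refer to it in section 5.5, stating that:

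- image quality exclusion, any segmentation correction or region selection, and parameter extraction are done on randomly coded images, without access to amyloid, clinical or cohort data;
- the resulting retinal values are locked before they are merged with the PET data;
- where feasible, and especially in the cognitively intact phase 2 groups, the examiner is not told amyloid status.

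It would help to say which retinal outputs are fully automated, so that readers can see where judgement enters. Masking SUVRcomp processing to the retinal results is optional, given the semi-quantitative PET classification with an independent cut-off.

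Cost: a random code for the images, a lock step and one paragraph, with no additional reader. Masking at acquisition will be only partial for patients whose dementia is evident in person, and the protocol should say so.

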3.2 Preparation, organization and management of phase 2 study

The primary objective of this study is to evaluate the diagnostic accuracy of three ophthalmological measures, selected based on the phase 1 study, for discriminating between A β -negative and A β -positive healthy cognitive-intact older adults and for discriminating between A β -negative cognitive-intact older adults and A β -positive MCI patients.

Methodology

Study cohorts:

1. Patients with amnestic MCI due to AD (A β -positive MCI), according to the NIA-AA diagnostic criteria, an MMSE 24 or higher, and with a positive CSF biomarker analysis or a positive amyloid-PET scan in the past or a positive amyloid-PET scan at inclusion, recruited via the memory clinic UZ Leuven (total number of amnestic MCI patients currently in follow-up = 64).
2. A β -positive cognitive-intact older adults. These will be recruited from the longitudinal cohort of older adults followed at the Laboratory for Cognitive Neurology described above. At inclusion

(between 2010-2015) 30 out of 180 participants were A β -positive. A positive CSF biomarker analysis or a positive amyloid-PET scan in the past or a positive amyloid-PET scan at inclusion is a prerequisite for inclusion in this group.

3. A β -negative cognitive-intact older adults, recruited from the same longitudinal cohort.

Study procedures:

cfr. Phase 1 study

Statistical analysis:

The primary analysis will be based on a contingency table, in which cognitively intact subjects will be classified according to one ophthalmological parameter and compared to the classification based on the A β PET. This will be done for the three parameters that have been selected based on the phase 1 data. The same will be done for the classification of the cognitively intact A β -negative cases versus the A β -positive MCI cases.

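### In phase 1 and in the phase 2 MCI contrast, amyloid status and cognitive impairment cannot be separated, so neither supports a claim of accuracy for amyloid positivity; only the cognitively intact contrast does.

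*Protocol*

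**What the plan says.** Protocol section 3 states the target: "The main contribution will consist of the examination of the validity of retinal biomarkers as a diagnostic measure for" amyloid positivity, validated against amyloid load on flutemetamol PET. It also describes the planned database as holding amyloid-positive and amyloid-negative "patients with different stages of cognitive impairment".

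The synopsis gives the sample as "90 individuals (35 amyloid-negative, 55 amyloid-positive"). The cohorts behind these totals are:

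- Phase 1, amyloid-positive (section 3.1): "Fifteen clinically probable AD patients, according to the National Institute of Aging (NIA)-Alzheimer's Association (AA) diagnostic criteria".
- Phase 1, amyloid-negative (section 3.1): "Fifteen A β -negative cognitive-intact healthy controls will be recruited from a longitudinal cohort". Both their amyloid-negative and their intact status are checked again at inclusion.
- Phase 2, impaired (section 3.2): amnestic MCI due to AD, with a positive CSF result, a past positive PET or a "positive amyloid-PET scan at inclusion, recruited via the memory clinic UZ Leuven".
- Phase 2, intact (section 3.2): amyloid-positive intact adults, and amyloid-negative "cognitive-intact older adults, recruited from the same longitudinal cohort".

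Section 8.1 sets 15 per group in phase 1 and 20 per group in phase 2.

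The statistical paragraph of section 3.1 takes the binary PET classification as the standard of truth for the cross-sectional studies. It ranks a wide range of eye measures by AUC and carries the best three into phase 2. Section 3.2 then tests each of the three in two contrasts: amyloid-positive v amyloid-negative among intact adults, and amyloid-positive MCI v amyloid-negative intact adults. Section 3.3 uses the same three parameters in the primary longitudinal analyses.

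**The concern.** If every amyloid-positive participant in a contrast is impaired and every amyloid-negative one is intact, the retinal difference between the groups may come from amyloid, from impairment and its accompanying neurodegeneration, or from both. No analysis of that contrast can tell which. Matching phase 1 controls on age, gender, education and apoE status does not help, because cognition is the factor that differs by design.

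This is plausible on the protocol's own account: its background section cites neuro-retinal thinning and microvascular change in AD patients, and neither need be specific to amyloid. Two consequences follow. Phase 1 may rank a marker of neurodegeneration above a marker of amyloid, and only the top three go forward to phase 2 and to the longitudinal analyses. And the sensitivity and specificity from the MCI contrast may be reported as accuracy for amyloid positivity, which they do not estimate.

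**Working it through.** **1. Reproduce the stated sample.** Inputs are the cohorts in sections 3.1 and 3.2 and the group sizes in section 8.1.

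- Amyloid-negative: 15 + 20 = 35.
- Amyloid-positive: 15 (AD) + 20 (MCI) + 20 (intact) = 55.
- Total: 35 + 55 = 90.

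This matches the synopsis exactly, so no further amyloid-negative group is planned.

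**2. Cross amyloid status with impairment.** Write a = positive and impaired, b = positive and intact, c = negative and impaired, d = negative and intact. The association is phi = (ad − bc) / √[(a+b)(c+d)(a+c)(b+d)].

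| Comparison | a | b | c | d | phi |
|---|---|---|---|---|---|
| Phase 1 | 15 | 0 | 0 | 15 | 225/225 = 1.0 |
| Phase 2, MCI contrast | 20 | 0 | 0 | 20 | 400/400 = 1.0 |
| Phase 2, intact contrast | 0 | 20 | 0 | 20 | not defined: no impairment to vary |
| Phase 2, all three groups | 20 | 20 | 0 | 20 | 400/800 = 0.50 |
| All 90 | 35 | 20 | 0 | 35 | 1225/1925 = 0.64 |

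Cell c is zero in every row. In phase 1 and in the MCI contrast, a model with an intercept, amyloid and impairment has rank 2 for 3 terms, so the two effects cannot be estimated apart. With all three phase 2 groups the rank is 3. The effects are then separable, but only if they are assumed to add, because the cell of amyloid-negative impaired people is empty.

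**3. Illustrate the size.** The documents give no retinal effect of impairment alone, so the shift is an assumption. Take a normally distributed marker with equal variances that shifts by δ standard deviations with impairment and not at all with amyloid. In either confounded contrast, the apparent AUC is Φ(δ/√2), and sensitivity and specificity at the midpoint cut-off are each Φ(δ/2).

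| Assumed δ | Apparent AUC | Sensitivity = specificity |
|---|---|---|
| 0.5 | Φ(0.354) = 0.64 | Φ(0.25) = 0.60 |
| 1.0 | Φ(0.707) = 0.76 | Φ(0.50) = 0.69 |
| 1.33 | Φ(0.940) = 0.83 | Φ(0.665) = 0.75 |

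Among people at the same cognitive stage, this marker has an AUC for amyloid of 0.50. The upper value of 1.33 is borrowed only as a familiar magnitude. In section 8.1 it is the assumed difference between amyloid-positive and amyloid-negative intact adults, so it is not evidence of an impairment effect.

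**The case against.** The strongest reply is that this is a legitimate staged design. Phase 1 is labelled exploratory and starts with clear cases against healthy controls. Phase 2 then tests the selected parameters in an independent cohort, and its intact contrast holds cognitive stage constant. A parameter that tracks only impairment should fail there. Sections 3.1 and 3.2 also name the groups compared quite openly. All of this stands, and it means the design as a whole is not invalid. It does not remove the point: the intact contrast tests only what phase 1 selected, so it cannot recover an amyloid-specific parameter ranked fourth, and it does not change what the MCI contrast estimates.

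Some stronger readings are tempting but not supported:

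- A reader might infer from section 3 that amyloid-negative impaired patients are promised. The sentence can equally describe the pooled sample, so it is unclear wording and not a firm contradiction. The confounding follows from the cohort definitions on either reading.
- A reader might take 0.50 as the marker's true AUC for amyloid in general. It holds only within one cognitive stage. Where impairment and amyloid are correlated, the AUC is not 0.50.
- A reader might say the test is meant for memory-clinic patients with impairment from other causes. Section 3 names presymptomatic recruitment, screening, early diagnosis and follow-up, and the intact contrast serves the presymptomatic aim directly.
- A reader might propose keeping MCI candidates whose inclusion PET is negative, as data already in hand. The protocol does not say that the eye examinations precede the PET result, and gives no number of such candidates.

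One further caveat: the AD and MCI groups may enter on CSF or a past scan, so an impaired participant could prove PET-negative at inclusion. The plan neither intends nor counts such cases.

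**Conclusion.** The point holds for phase 1 and for the MCI contrast. By plan, 0 of 35 impaired participants are amyloid-negative and 0 of 35 amyloid-negative participants are impaired, so both contrasts measure amyloid and impairment together. They can show how well a parameter separates amyloid-positive AD dementia or MCI from amyloid-negative healthy adults. They cannot show accuracy for amyloid positivity, although sections 3 and 3.1 frame them in those terms. Only the intact contrast (20 v 20) tests amyloid with cognitive stage held constant.

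The counts come straight from the protocol. The AUC range of 0.64 to 0.83 rests on an assumed impairment-only shift of 0.5 to 1.33 SD and a normal, equal-variance marker; it shows what could happen and is not an estimate. The matter is worth correcting because it changes what the trial may conclude and costs almost nothing, but the study remains useful without it.

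**What to change.** 1. In the statistical paragraphs of sections 3.1 and 3.2, state that phase 1 and the MCI contrast estimate discrimination of amyloid-positive AD dementia or MCI from amyloid-negative healthy adults, and that accuracy for amyloid positivity will be claimed only from the intact contrast. Reword the database sentence in section 3 so that it does not imply impaired amyloid-negative patients.
2. Add, as a supportive analysis of the three selected parameters, amyloid-positive MCI v amyloid-positive intact adults (20 v 20, both groups already planned). Report SUVRcomp for each group beside it. State that the groups differ in recruitment source (memory clinic v research cohort) and possibly in amyloid load, so the comparison indicates the contribution of cognitive stage but does not cleanly apportion it. If the SAP already contains this comparison, only the wording change remains.

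The cost is a few sentences and one extra table from data the plan already collects. No participants or procedures are added. The downside is a narrower claim from phase 1 and the MCI contrast.
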